7.3. Primary endpoint

- (a) Determination of the Ka for Bicillin® L-A administered via the SC route.

7.4. Secondary endpoints

- (a) Pain scores related to administration of Bicillin® L-A for the SC and IM routes.
- (b) Defined AEs related to SC and IM routes of administration of Bicillin® L-A.
- (c) Time above the MIC for Bicillin® L-A administered via the SC and IM routes.

7.5. Study stopping rules

Individual subjects will be stopped from continuing in the trial if they:

- (a) display signs or symptoms of a penicillin allergy.
- (b) have a serious adverse reaction.
- (c) request discontinuation.

An individual subject who wishes to stop the trial after first dosing will be withdrawn from the study and followed up as per the withdrawal section 8.5.

The trial can be stopped at any stage at the discretion of:

- (a) the Principal Investigator (PI)
- (b) the study sponsor
- (c) suspected unexpected serious adverse reaction (SUSAR), after discussion with the ethics committee

8. SELECTION AND WITHDRAWAL OF PARTICIPANTS

8.1. Study population

Participants will meet **all** the inclusion criteria and **none** of the exclusion criteria.

8.2. Study numbers

15 participants are required to perform this study.

8.3. Study inclusion criteria

Participants who meet **all** the inclusion criteria are eligible to be a participant in the trial:

- (a) Male aged 18 - 65 years at the time of screening.

- (b) BMI between 18.5kg/m² and 25kg/m².
- (c) No history of chronic renal impairment or significant liver dysfunction.
- (d) No prior documented allergy to penicillin, cephalosporin antibiotics.
- (e) Participants who are considered likely to adhere to the trial guidelines for the duration of the trial.
- (f) Sign and dated informed consent in accordance with Good Clinical Practice (GCP) / Declaration of Helsinki (DoH) (Appendix 5).

8.4. Study exclusion criteria

Patients who meet **any** of these criteria are not eligible for participation in the trial:

- (a) Currently taking penicillins or Use of any penicillin-based antibiotics from screening through to the final study visit. The use of probenecid, NSAIDs, or other medications which may significantly alter the Bicillin® L-A PK will also not be permitted within 14 days prior to study drug administration until completion of the final follow-up visit, with the exception of occasional paracetamol and ibuprofen use.).
- (b) Participation in another clinical trial in the three months preceding the trial.
- (c) Planned participation in another clinical trial concurrently.
- (d) Planned operation/absence from the study site during the duration of the study.
- (e) Known penicillin allergy or soy allergy.
- (f) History of any clinically significant hip/gluteal surgery/radiotherapy.
- (g) Use of any prescription medication or over-the-counter medication, herbal products, vitamins or minerals, within 7 days prior to study drug administration until completion of the final follow-up visit, unless in the opinion of the Principal Investigator or delegate the medication will not compromise participant safety or interfere with study procedures or data validity
- (h) Participants must be non-smokers and must not have used any tobacco products within 1 month prior to screening

8.5. Participant withdrawal

8.5.1. Process of withdrawal

Participants will be able to withdraw from the study at any stage without consequence. In the event of a participant withdrawal, they will be treated without prejudice; reasons for withdrawal will be recorded if volunteered. They will not need to have any specific treatment in the event of withdrawal. i.e., no antidote medication.

8.5.2. Data to be collected for withdrawn participant(s)

Participants who withdraw from the trial will have all data up to point of withdrawal included in the trial results.

8.5.3. Replacement of participants

Withdrawal of a participant will not result in replacement recruitment unless the withdrawal occurs before the first injection because of the cross-over methodology of the trial.

8.5.4. The follow-up of withdrawn participants

The withdrawn participant will still be able to receive medical care if related to the investigational product as per the GCP guidelines. If they have received a dose of Bicillin® L-A, they will be monitored for a minimum of 30 days.

9. STUDY PROCEDURES

9.1. Description of assessments and procedures

9.1.1. Informed consent

Signed written consent must be obtained from the participant in accordance with GCP guidelines; informed consent is an ongoing process throughout the trial and may be withdrawn freely at any time by the participant without reason.

9.1.2. Eligibility criteria

Participants must meet all inclusion criteria and no exclusion criteria to be eligible to participate.

9.1.3. Medical history / examination

During screening, participants will have history examination performed which will include, but is not limited to:

- (a) History of renal disease.
- (b) History of liver disease.
- (c) History within the last 12 months of gluteal intramuscular or subcutaneous injection or operation.
- (d) Adverse reaction to injections / phlebotomy.
- (e) Known allergies.
- (f) Screening physical exam, including vital signs, height, weight, and auscultation.

9.1.4. Laboratory tests

Baseline blood testing will occur during screening and on injection days via means of phlebotomy. The following standard testing will be performed:

- (a) Haematology: complete blood count.
- (b) Clinical chemistry: urea, glucose, creatinine, sodium, potassium, chloride and bicarbonate, lactate dehydrogenase, calcium, total protein, magnesium, phosphate, albumin, cholesterol,

and uric acid [eGFR >90ml/min/m² will be considered normal using the CKD-EPI and the absence of albuminuria on dipstick].

- (c) Liver function tests (only at screening): aspartate aminotransferase, alanine aminotransferase, alkaline phosphatase, total bilirubin, gamma-glutamyl transferase [$<1.5 \times$ ULN (ALT, GGT) will be considered normal].
- (d) Serology (only at screening): HIV, Hepatitis B and C.

Urine dipstick for blood, protein, leukocytes, nitrite, and drug screening along with breath alcohol testing will be conducted at screening and on injection days.

Participants who undergo screening, who have a significant abnormality detected, will be referred to their general practitioner for further investigation and management as deemed appropriate by the PI or delegate.

9.1.5. Dried blood spot assays to measure penicillin

Dried blood spots (DBS) have been used for decades in clinical application, the most common being the Guthrie test. Over the last decade, refinement of the DBS technology has allowed the expansion of the gamut of testing possible with the DBS. Hepatitis B, HIV, and malaria parasites are all able to be detected with DBS in addition to therapeutic drug monitoring. The DBS has several advantages. The blood required is minimal: each standard sample is only 10-20 μ L instead of the usual 3000-10000 μ L (3-10ml) required for traditional venesection in adults. The complications from venepuncture include inadvertent arterial puncture, haematoma, thrombophlebitis, and bruising. DBS, sampled from the fingers, are not associated with these complications. Development of the DBS system has allowed for more ethical PK studies in children. This method has recently been validated for penicillin, ceftriaxone, and ertapenem. DBS samples can be taken serially and impregnated onto filter paper which is stored with desiccant without the need for processing of plasma and cell pellets. A small diameter disc can be subsequently punched out from the filter paper and the drug eluted into a liquid matrix prior to liquid chromatography-mass spectroscopy (LC/MS).⁷⁶⁻⁷⁸

9.1.6. Pain scoring

Pain scoring will be measured using the numeric rating scale (NRS), which is a valid method for recording pain in this setting.⁷⁹ . The NRS has been validated in adults for recording pain; the scoring system has 11 (0-10) different values anchored by terms describing pain severity extremes: 0=none, 1-3=mild, 4-6=moderate, and 7-10=severe. A score of 10 indicates the worst pain imaginable. The NRS is a widely accepted tool for the quantitative assessment of pain, and has the ability to detect significant changes in pain and is comparative to other methods of pain reporting such as the visual analogue scale, whilst having the advantage of being easier to record, with less chance of error.⁷⁹ As mentioned in section 6.13, there is variability in the definition of 'significant reduction' in pain. With a moderate pain score of NRS=4, a change of 1.3 units are required to be

'minimally clinically significant'.⁶³ Additionally, participants will describe the character of the pain using the phrases "throbbing", "dull", or "sharp". They will be asked if the pain prevents them from undertaking any desired activities. E.g. walking. Pain will be assessed at pre-determined intervals (as described earlier) and if present, continue to be assessed at each follow-up visit until pain levels return to zero. It will be noted if additional medication is taken e.g. paracetamol or ibuprofen.⁸⁰

9.1.7. Monitoring of skin irritation

The participant will be questioned regarding symptoms of pain, character, itchiness, pallor or erythema bleeding, and heat. Participants will be inspected by a study team member for evidence of skin erythema at day 1 and 2, with continued visual inspection if there was presence of pain or irritation as reported by the participant (days 4, 7, 14, 21, 28) until resolution. Area of irritation or erythema if present will be measured in length and width.

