The risk of IV injection is present in SC injections, although the rates of inadvertent vascular damage are significantly lower than XX? owing to the reduced blood supply of SC tissue. SC granulomas are a common incidental finding on imaging; uncommonly, SC injections are thought to be responsible for the development of calcific granulomas and fat necrosis.⁴⁸ Kawai et al., 2014, reported on the rate of injection site reaction to depot SC injection of leuprorelin acetate. Over a 5-year period at Tokai University Hospital, they identified 13 out of 335 (3.88%) of patients had a reaction to the depot injection. Eleven cases of SC induration were reported, as well as one ulceration and one SC ulceration and mass. Additionally, they examined case reports from 1999 onwards and identified 37 cases of SC granuloma formation. They noted that almost half of the granulomas spontaneously resolved (15/37).⁷⁴

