Injection Site: Injection site reactions (including pain, inflammation, lump, abscess, necrosis, oedema, haemorrhage, cellulitis, hypersensitivity, atrophy, ecchymosis, and skin ulcer); neurovascular reactions (including warmth, vasospasm, pallor, mottling, gangrene, numbness of the extremities, cyanosis of the extremities, and neurovascular damage).

Metabolic: Elevated BUN, creatinine, and SGOT.

Musculoskeletal: Joint disorder; periostitis; exacerbation of arthritis; myoglobinuria; rhabdomyolysis.

Nervous System: Nervousness; tremors; dizziness; somnolence; confusion; anxiety; euphoria; transverse myelitis; seizures; coma.

A syndrome manifested by a variety of CNS symptoms such as severe agitation with confusion, visual and auditory hallucinations, and a fear of impending death (Hoigne's syndrome), has been reported after administration of benzylpenicillin procaine and, less commonly, after injection of the combination of benzylpenicillin benzathine and benzylpenicillin procaine. Other symptoms associated with this syndrome, such as psychosis, seizures, dizziness, tinnitus, cyanosis, palpitations, tachycardia, and/or abnormal perception in taste, also may occur.

Respiratory: Hypoxia; apnoea; dyspnoea.

Skin: Diaphoresis.

Special Senses: Blurred vision; blindness.

Urogenital: Neurogenic bladder; haematuria; proteinuria; renal failure; impotence; priapism.

DOSAGE AND ADMINISTRATION

Use a concentration of 442 mg/mL when measuring part doses. The quantity of benzathine benzylpenicillin is based on 1,200 Units/mg potency.

Streptococcal (Group A) upper respiratory infections (for example, pharyngitis)

A single injection of 1,200,000 Units for adults.

A single injection of 900,000 Units for older children.

A single injection of 300,000 to 600,000 Units for infants and for children under 27 kg.

Venereal infections

Syphilis - Primary, secondary and latent - 2,400,000 Units (1-dose). Late (tertiary including neurosyphilis) - 2,400,000 Units at 7-day intervals for three doses.

Version: pfpbaci10917

Superseded: pfpbaci10317
Page 7 of 9

Congenital (with normal CSF) - under 2 years of age: 50,000 Units/kg body weight; ages 2-12 years; adjust dosage based on adult dosage schedule.

Yaws, bejel and pinta - 1,200,000 Units (single injection).

Prophylaxis - for rheumatic fever and glomerulonephritis

Following an acute attack, benzathine benzylpenicillin (parenteral) may be given in doses of 1,200,000 Units once a month or 600,000 Units every 2 weeks.

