20.7. Appendix 7- Study Schedule of Assessments

	Screen	Period 1 and Period 2												Washout Period	Follow-up Period		
	2 weeks	Day 0					Day 1	Day 2	Day 3	Day 5	Day 7	Day 14	Day 21	Day 28	Day 42	4 weeks	14 Days after Completing Period 2
Event ▼	Study Hour ►	Pre-dose	0 h	2	6	12	24	48	72								
Informed Consent	X																
Inclusion/Exclusion Criteria	X	X															
Demographics																	
Medical History	X																
Height	X																
Physical Exam (incl. weight)	X																
Vital Signs	X	X		X	X	X											
Clinical Laboratory Tests	X	X															
HIV, Hepatitis B/C Testing	X																
Urine Drug / Alcohol Breath Test	X	X															
Dried Blood Sampling PK Sample		X		X	X	X	X	X	X	X	X	X	X	X	X		
PK Blood Sample (from a vein)						X						X					
Pain Score			X	X	X	X	X	X	X ²	X ²	X ²	X ²	X ²	X ²	X ²		
Monitoring of Skin Irritation							X	X	X ²	X ²	X ²	X ²	X ²	X ²	X ²		
Ultrasound Scan of Injection Site			X										X				
Study Medication Administration			X														
Adverse Events		←															→
Record Current Medications	←																→
In Clinic Confinement		←				→											
Outpatient Visit	X						X	X	X	X	X	X	X	X	X		
Telephone Call Follow-up																	X

¹ Participants should be resting in a supine position for at least 5 minutes prior to and during the measurement of vital signs. When vital signs are scheduled at the same time as blood draws, the vital signs will take priority. Additional vital signs may be performed as clinically indicated.

² Assessments performed only if pain or irritation was recorded at the previous visit.

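### Section 9.1.7 does not solicit swelling, induration or a lump for either route, so a painless local reaction is captured only by open AE recording or one follow-up ultrasound

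*Protocol*

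**What the plan says.** Section 9.1.7 sets four things.

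- **Questions:** "The participant will be questioned regarding symptoms of pain, character, itchiness, pallor or erythema bleeding, and heat".
- **Early inspection:** "Participants will be inspected by a study team member for evidence of skin erythema at day 1 and 2".
- **Later inspection:** "continued visual inspection if there was presence of pain or irritation as reported by the participant (days 4, 7, 14, 21, 28", until resolution.
- **Measurement:** "Area of irritation or erythema if present will be measured in length and width".

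Appendix 7 applies the same condition to skin monitoring after day 2: "Assessments performed only if pain or irritation was recorded at the previous visit". It places those conditional checks on days 3, 5, 7, 14, 21, 28 and 42.

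Elsewhere the protocol describes the signs that 9.1.7 leaves out. Section 6.14.1 counts localised swelling among the commonest side effects of IM injection. The same section gives a series on a subcutaneous leuprorelin depot, with 13 of 335 patients (3.88%) reacting: "Eleven cases of SC induration were reported, as well as one ulceration and one SC ulceration and mass". The product information in Appendix 1 lists "Injection site reactions (including pain, inflammation, lump, abscess, necrosis, oedema, haemorrhage" and further local effects.

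Two other provisions can pick up local reactions. Section 11.2 records every adverse event that staff observe or the participant reports. The synopsis lists ultrasound-detected local changes by route as a secondary measure, with a follow-up scan four weeks after injection.

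**The concern.** The type, number and severity of adverse events by route is a secondary measure, and the secondary hypothesis in section 7.2 is that SC tolerability is better than or comparable to IM. Local reactions are central to that comparison.

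As written, a participant with a firm, painless lump under normal skin answers no to every question. He shows no erythema on days 1 and 2, and he triggers no later inspection. Nothing in 9.1.7 has anyone feel the site or record a size. The class of reaction that the protocol's own background describes for both routes is therefore left to chance recording. A reaction not recorded during follow-up cannot be recovered at analysis.

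A comparison that misses a class of reaction will tend to show no difference in that class, and that is one of the two outcomes the hypothesis counts as success.

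**Working it through.** **1. What is solicited, set against what the protocol describes**

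| Sign | Asked, inspected or measured in 9.1.7 | Described elsewhere in the protocol |
|---|---|---|
| Pain, itch, erythema or pallor, bleeding, heat | Asked; erythema inspected and measured | Yes |
| Swelling or oedema | No | Common IM reaction (6.14.1); SC teicoplanin (6.9); this product (Appendix 1) |
| Induration | No | SC leuprorelin depot (6.14.1) |
| Lump or mass | No | This product (Appendix 1); SC leuprorelin depot (6.14.1) |

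The missing signs appear for both routes, so the gap is in the instrument as a whole.

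**2. The cited subcutaneous depot series**

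- Stated figure: 13/335 = 0.0388, or 3.88%. This reproduces.
- Types: 11 induration + 1 ulceration + 1 ulceration with mass = 13.
- Induration as a share of reactions: 11/13 = 84.6%. Adding the mass case: 12/13 = 92.3%.
- Induration as a share of patients: 11/335 = 3.3%.

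These counts are for another drug and are per patient. The protocol does not say how many injections each patient had. Applying the rate to single BPG injections is therefore an assumption.

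**3. What that could mean for 15 SC injections**

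Expected cases = 15 × p. Chance of at least one case = 1 − (1 − p)^15.

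| Induration rate p | Source | Expected cases | Chance of at least one |
|---|---|---|---|
| 3.3% | Cited series, other drug | 0.49 | 39% |
| 10% | Assumption | 1.5 | 79% |
| 20% | Assumption | 3.0 | 96% |
| 50% | Assumption | 7.5 | >99% |

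The protocol gives no rate for subcutaneous BPG, so the table shows a range and not a forecast.

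**4. Effect on the comparison between routes**

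Let a sign have true rates p_SC and p_IM, and let it be recorded with probabilities c_SC and c_IM. The expected observed difference is c_SC × p_SC − c_IM × p_IM.

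- If capture is equal (c_SC = c_IM = c < 1), this is c × (p_SC − p_IM). The difference shrinks towards zero, whichever route is worse.
- If capture differs by route, the sign of the distortion depends on four quantities, none of which the documents give.

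So under-recording can help a finding of comparable tolerability, but a net advantage for one route cannot be computed.

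**5. Inspection days**

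Sections 9.1.7 and Appendix 7 agree on days 1 and 2. After that, 9.1.7 lists days 4, 7, 14, 21 and 28, while Appendix 7 lists days 3, 5, 7, 14, 21, 28 and 42. Day 4 is in the text only; days 3, 5 and 42 are in the schedule only.

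**The case against.** A reader might infer that the omission tilts the tolerability comparison towards SC. The documents do not support that. The same questions and inspection apply to both routes in a crossover, swelling is named as a common IM reaction, and the product information listing lump and oedema is for a product labelled for deep IM use. Nothing in the protocol says that a lump is the expected sign of this suspension in fat, or that an IM depot seldom shows at the surface.

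The evidence on induration is also indirect. It comes from leuprorelin, at an overall rate of 3.88%. The protocol's one human remark on inadvertent subcutaneous BPG (section 6.2) is longer discomfort, which is pain and is scored until it returns to zero. The piglet penicillin study in section 6.7 is reported as showing no adverse effects in the IM and SC comparison. A reader might infer that several SC events would be lost, but that needs assumed rates of 20% or more.

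Capture is not absent either. Section 11.2 covers events that staff see as well as those volunteered. Participants are observed for 12 hours and attend visits up to day 42, and ultrasound changes are compared between routes. An investigator might also count a lump as irritation, a term that 9.1.7 does not define. Appendix 3 leaves the electronic forms still to be developed.

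All of this stands, and it limits the point. It does not remove it. Open recording is unsolicited for these signs. The follow-up ultrasound is one late look, which can miss reactions already resolved and gives no onset or duration. Forms built from 9.1.7 as written would carry the same gap.

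On the days, the ±1 day sampling window for day 5 in Table 4 makes a day-4 attendance possible, but it does not make the two lists agree.

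**Conclusion.** The point holds as a gap in solicitation that affects both routes. Section 9.1.7, followed exactly, neither asks about nor looks for painless swelling, induration or a lump, and it does not follow one up. The protocol's own background names these signs for IM injection, for this product and for a subcutaneous depot of another drug.

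The size is uncertain. It is about 0.5 induration cases in 15 SC injections if the leuprorelin rate carried over, and more only under assumed higher rates. Incomplete capture can favour a conclusion that SC is comparable; the direction and size of any net bias between routes cannot be derived. The primary PK comparison is not affected. The mismatch in inspection days is a small, separate inconsistency. Overall this is an inexpensive improvement to a secondary comparison, not a fault that invalidates it.

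**What to change.** In section 9.1.7:

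1. Add swelling and induration or lump to the questions.
2. Add a brief palpation of the injection site, recording the largest diameter of any finding.
3. Do both identically for the two routes, at the existing visits in both periods, and not conditional on reported pain or irritation.
4. Reconcile the inspection days in 9.1.7 with those in Appendix 7, and adjust the Appendix 7 footnote to match item 3.

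The cost is a few form fields and roughly a minute per visit. Appendix 7 has nine outpatient visits per period after dosing (days 1, 2, 3, 5, 7, 14, 21, 28 and 42), so about 9 × 2 = 18 minutes per participant and 18 × 15 = 270 minutes for the trial. No visits or staff are added. The downside is that more minor local findings will be recorded.

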9.1.8. Contraception

It is recommended that male participants with a female partner of child-bearing potential, use a condom for all sexual intercourse for the entire duration of the study until completion of all follow-up visit

9.1.9. Sampling schedule

It is expected the study will occur over an 18-week period. There will be a maximum of 26 DBS samples taken from each participant through the study period. Additionally, baseline blood tests will be performed in the screening period. A serum sample will be taken at 12 hours and at 14 days post-injection to compare penicillin levels to DBS. Participants will be recruited in month 1; after consent and screening tests, they will then be randomised to receive IM or SC Bicillin® L-A in month 1 as per the schedule (a-e):

(a) Enrolment and screening (2 weeks).

Potential participants will be screened according to the clinical criteria as described in section 6.5. They will then undergo the consent process, the required screening including history, and examination and screening blood tests as outlined in section 9.1.4-9.1.5. If any significant abnormalities are found on screening, they will be referred as clinically appropriate for further testing via their general practitioner and exit the study. Those who fulfil all inclusion and no exclusion criteria will then be blinded and randomised to Group A or Group B (see Table 3).

(b) Administration period 1 (6 weeks).

Participants will be randomised to either the SC or IM administration of Bicillin® L-A in the upper outer quadrant of buttock at day zero. The IMP (Bicillin® L-A) will be prepared as per the manufacturer's instruction in the product information sheet. Injection will occur with a 20G needle of appropriate length. The route of administration will be confirmed via real-time ultrasound imaging; the procedure is outlined in section 10.6. DBS samples will be taken at: baseline, then t=2,

6, 12, and 24 hours, followed by day 2, 3, 5, 7, 14, 21, 28, and 42. There is some flexibility in sampling times as demonstrated in Table 4 below. Pain scoring will be taken routinely at: baseline, t=2, 6, 12, 24, 48, and 72 hours, then at day 5, 7, 14, 21, 28, and 42 if injection-associated pain is recorded at the prior visit. Venesection will be conducted at baseline, 12 hours after the dose of BPG and at day 14 for baseline biochemical and haematological profile and to demonstrate concordance between plasma and DBS penicillin concentrations.

(c) Washout period (4 weeks).

Participants will undergo a washout period of at least 28 days after administration period 1.

(d) Administration period 2 (6 weeks).

After the washout period, participants will receive alternate administration of IM or SC Bicillin® L-A, dependent on the route of administration in period 1. The IMP (Bicillin® L-A) will be prepared as per the manufacturer’s instruction in the product information sheet. Injection will occur with the 20G needle supplied as part of the Bicillin® L-A product. The route of administration will be confirmed via real-time ultrasound imaging. The procedure is outlined in section 10.6. DBS samples will be taken at: baseline, t=2, 6, 12, and 24 hours, followed by day 2, 3, 5, 7, 14, 21, 28, and 42. There is some flexibility in sampling times as demonstrated in Table 4 below. Pain scoring will be taken routinely at: baseline, t=2, 6, 12, 24, 48, and 72 hours, then at day 5, 7, 14, 21, 28, and 42 if injection-associated pain is recorded at the prior visit. Venesection will be conducted on days 0 and 14 to verify the DBS levels.

(e) Post-sampling telephone follow-up (2 weeks).

Participants will be followed up after a 14-day period by telephone to confirm no persisting AEs; if present, they will be formally reviewed by a study team member.

Table 4: Sampling schedule for both administration periods 1 & 2

T: hrs (days)	0	2	6	12	24 (1)	48 (2)	72 (3)	120 (5)	168 (7)	336 (14)	504 (21)	672 (28)	1008 (42)
DBS	Y	Y	Y	Y	Y	Y	Y	Y	Y	Y	Y	Y	Y
Sampling window [‡]	-	±5 min	±15 mins	±30 mins	±4 hours	±8 hours	±12 hours	±1 day	±1 day	±2 days	±2 days	±2 days	±2 days
Pain score	Y	Y	Y	Y	Y	Y	Y	Y*	Y*	Y*	Y*	Y*	Y*
Venesection	-	-	-	Y	-	-	-	-	-	Y	-	-	-
USS	Y	-	-	-	-	-	-	-	-	-	-	Y	-

DBS = dried blood spot; Y = yes; * = possible measurement; USS = ultrasound scan of injection site (see appendix 8)
; [‡] = time in minutes/hours/days following Bicillin® L-A injection.

A study sampling schedule from screening through to follow up phone call is included as Appendix 7 for ease of reference.

